The following sample size calculations were based on comparison of the mean difference between groups (or arms) on a continuously measured outcome (or continuous variable). The sample size was fixed and detectable EF (or Cohen's D) was calculated. The detectable point difference for a continuous outcome was then calculated by multiplying EF and SD for the outcome measure.

Specific Aim 1.1: to test the hypothesis that HIN performance correlates with CAP amplitudes in anesthetized humans with Normal OHC function.

n = 52 subjects

Statistical Methods: described in detail in the Data Analysis section of the Research Strategy.

- 1. ANOVA to determine whether anesthetized subjects exhibit less variability than nonanesthetized subjects
- 2. Univariate and multivariate models to determine the relationship between mean CAP amplitudes and the other independent variables listed in Table 3 in all subjects
- ANCOVA or the regression model with indicator variable for Difficulty HIN vs. No Difficulty HIN groups will be utilized to compare statistically significant differences in anesthetized CAP amplitudes between the two groups
- 4. Cognitive and central auditory processing will be similarly analyzed to control for higher order effects on HIN
- 5. Multivariate regression models will be used to examine the interaction effect of two HIN groups with other independent variables (age and gender for example) on the dependent variable of mean CAP amplitudes

Power analysis: An ANCOVA model with 80% power on a continuously measured outcome assuming a significance level of 0.05 and a two group sample size of 52 (n=26 in each of the Difficulty HIN vs. No Difficulty HIN groups) will detect an effect size (EF) of 0.8 or above. We will able to detect a trued difference of 0.13 μ V between two groups for the primary outcome of CAP amplitude assuming our current standard deviation of 0.166 for CAP amplitudes (triptodes) measured in the 57 subjects with PTA<12.5 dB HL in our existing database.

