- subjects within each group will be categorized by _{hf}PTA as either Normal (0-12.5 dB HL), Minimal SNHL (12.6-25 dB HL), or Mild SNHL (< 26 dB HL)
 - a. ANOVA will be used to determine statistically significant differences in objective HIN performance, OHC function, and AN function
- 3. ANCOVA will be run to compare these variables among HA feature or control groups

Power analysis: Again, using mean CAP amplitude as the primary outcome, two hundred (200) subjects per group with equal (100) number of subjects with or without difficulty HIN, we will be able to detect 0.28 EF difference among groups with 80% power and a significance of 0.05. This can be translated to a 0.046 SNR Loss difference on HIN performance (QuickSIN) measured by CAP amplitude (standard deviation= 0.166). For the experimental group and HIN difficulty interactions, we will be able to detect an EF of 0.325 which is equivalent to 0.054 μ V on CAP amplitude.

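### The Aim 2 power analysis labels 0.046 a QuickSIN SNR Loss difference, but it is 0.28 times the CAP-amplitude SD and therefore 0.046 µV

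*SAP*

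**What the plan says.** The opening paragraph of the SAP sets out how every detectable difference is obtained. The sample size is fixed first: "The sample size was fixed and detectable EF (or Cohen's D) was calculated". The conversion to raw units follows: "The detectable point difference for a continuous outcome was then calculated by multiplying EF and SD for the outcome measure".

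The Specific Aim 1.1 power analysis gives the only SD in the document, "our current standard deviation of 0.166 for CAP amplitudes (triptodes) measured in the 57 subjects with PTA<12.5 dB HL", and uses it for a difference in µV.

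The Specific Aim 2 power analysis is framed as "using mean CAP amplitude as the primary outcome". It takes 200 subjects per group, 80% power and a significance level of 0.05, arrives at an effect size of 0.28, and converts it with the same 0.166: "This can be translated to a 0.046 SNR Loss difference on HIN performance (QuickSIN) measured by CAP amplitude". The next sentence converts the interaction effect size with the same SD, "we will be able to detect an EF of 0.325 which is equivalent to 0.054", and gives that result in µV on CAP amplitude.

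The Aim 2 statistical methods list objective HIN performance, OHC function and AN function as variables to be compared, and then state: "ANCOVA will be run to compare these variables among HA feature or control groups". The Aim 2 subjects are classed by hfPTA as "Normal (0-12.5 dB HL), Minimal SNHL (12.6-25 dB HL), or Mild SNHL".

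**The concern.** An effect size has no unit, so its product with an SD takes the unit and the outcome of that SD. Here the SD belongs to CAP amplitude, an electrophysiological measure in µV. The result is attributed to QuickSIN SNR loss, a different measure on a different scale. The added phrase about CAP amplitude does not connect the two, because the SAP gives no conversion.

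The label matters because Aim 2 asks whether hearing-aid strategies meant to improve HIN performance compensate for OHC or AN dysfunction, and objective HIN performance is one of the outcomes compared among groups. The sentence at issue is the only place where the SAP says how small a difference on that outcome it could detect. Read as written, it promises 80% power for a 0.046 SNR Loss difference, which nothing in the document supports.

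**Working it through.** **Inputs, all from the SAP**
- Rule: detectable difference = effect size × SD of the outcome (opening paragraph).
- SD = 0.166, for CAP amplitude (Aim 1.1 power analysis; repeated under Aim 2).
- Aim 2: 200 per group, power 80%, significance level 0.05, effect size 0.28; interaction effect size 0.325.
- Aim 1.1: effect size 0.8.
- QuickSIN SD: not given.

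**1. Reproduce the effect size.** For two groups of n = 200, two-sided (the SAP does not state sidedness, but two-sided reproduces its figure):

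d = (z₀.₉₇₅ + z₀.₈₀) × √(2/n) = (1.960 + 0.842) × √(2/200) = 2.802 × 0.100 = 0.280.

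The t-test solution is 0.281. The stated 0.28 is right for one unadjusted comparison of two groups of 200.

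**2. Reproduce the raw differences.**

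| Place | Effect size × 0.166 | Product | As printed |
|---|---|---|---|
| Aim 1.1 | 0.8 × 0.166 | 0.133 | 0.13 µV |
| Aim 2, interaction | 0.325 × 0.166 | 0.054 | 0.054 µV on CAP amplitude |
| Aim 2, main comparison | 0.28 × 0.166 | 0.0465 | 0.046 SNR Loss (QuickSIN) |

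All three are products with the CAP-amplitude SD. Only the third carries another outcome and unit.

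**3. What the label would require.** For 0.046 to be the QuickSIN difference at effect size 0.28, the QuickSIN SD would have to be 0.046 / 0.28 = 0.164. That is the CAP SD recovered from a rounded product, not independent support for the figure.

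**4. Illustration with assumed QuickSIN SDs.** These SDs are assumptions; the document gives none. Power is for a two-sided t test at 0.05 with 200 per group, counting both rejection tails. The standardized difference is 0.046 / SD.

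| Assumed SD (dB) | Difference at effect size 0.28 | 0.046 dB as standardized difference | Power for a true 0.046 dB |
|---|---|---|---|
| 1 | 0.28 dB | 0.046 | 7.4% |
| 2 | 0.56 dB | 0.023 | 5.6% |
| 3 | 0.84 dB | 0.015 | 5.3% |

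**5. Two qualifications on the corrected µV figure.**
- *Population.* The 0.166 comes from subjects with PTA below 12.5 dB HL, whereas Aim 2 also includes Minimal and Mild SNHL. If the CAP SD in the wider range were between 0.12 and 0.25 (assumed), the detectable difference would run from 0.28 × 0.12 = 0.034 µV to 0.28 × 0.25 = 0.070 µV.
- *Number of groups.* The SAP speaks of differences among groups. If 1,000 subjects at 200 per group means five groups (1,000 / 200 = 5; inferred, not stated), an overall F test has noncentrality 11.99 at 80% power, so f = √(11.99 / 1,000) = 0.110. With two extreme groups and the other three midway, that is d = 0.110 × √10 = 0.346 (before rounding f). Bonferroni-adjusted pairwise tests would need d = 0.335 for 4 comparisons and 0.367 for 10.

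**The case against.** The strongest reply is that this is one wrong label and the design does not depend on it. The multiplication is right, the effect size of 0.28 reproduces, and the sample size stands. The power analysis names CAP amplitude as its outcome, the disputed sentence quotes the CAP SD, and the following sentence is in µV, so a careful reader can work out what was meant. All of that is true, and it limits the weight of the point. It does not make the sentence correct. The sentence names a different instrument, and nothing elsewhere in the SAP corrects it.

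It can also be said that a plan powered on CAP amplitude need not give a raw detectable difference for every other variable. OHC function has none either, and a QuickSIN SD may appear in the Research Strategy, which is not shown. This is fair: omitting a QuickSIN figure would not be a fault in itself. The fault is that one is stated and is wrong.

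The power figures for a 0.046 dB difference rest on assumed SDs and show only how far the label misleads. They do not measure any loss of power in the trial. Likewise, the document does not show that the CAP SD differs in subjects with hearing loss, and the five-group reading is inferred. Both are qualifications to state, and the main point does not rest on them.

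**Conclusion.** The concern holds. The Aim 2 figure of 0.046 is a CAP-amplitude difference in µV, and its attribution to QuickSIN SNR loss is wrong. This follows from the SAP's own rule, its own SD and its own parallel sentence, without outside assumptions. The SAP therefore contains no valid detectable difference in SNR-loss units. How large such a difference would be depends on a QuickSIN SD that the document does not give.

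The error does not change the effect size, the sample size or any analysis. It misstates what the study can detect on an outcome central to Aim 2, so it should be corrected.

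**What to change.** In the Specific Aim 2 power analysis, state the detectable difference as 0.046 µV on CAP amplitude and delete the reference to SNR Loss and QuickSIN. If a statement about QuickSIN is wanted, give it separately in dB, as the effect size times a stated and sourced QuickSIN SD.

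In either case add two short notes:
- 0.28 is the effect size for a single unadjusted comparison of two groups of 200.
- The SD of 0.166 comes from subjects with PTA below 12.5 dB HL and is assumed to hold for the Minimal and Mild SNHL subjects of Aim 2.

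The relabelling and the notes cost wording only, with no change to sample size or procedures. The optional QuickSIN figure needs one sourced SD, which this document does not contain.

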This effect size is less than desired for a large clinical trial. However, this size is appropriate given that the aim is to determine which method is the most effective in accurately measuring CAP in humans. Further, it is similar to the sample sizes of persons with $_{hf}$ PTA < 12.5 dB HL in the database of our existing clinical trial using triptodes (n= 57) and TM wick electrodes (n= 59) in unanesthetized humans to which this comparison will be made. The ensuing experiments will increase the subject size and reduce the EF.

Specific Aim 1.2: to test the hypothesis that HIN performance is primarily governed by OHC, rather than AN function.

n = 600 subjects

Statistical Methods: described in detail in the Data Analysis section of the Research Strategy.

- subjects will be rank ordered by hfPTA, and either parametric or nonparametric coefficients of correlation will be run between subjective HIN difficulty, objective HIN assessments, OHC function, AN function, central auditory processing, and cognitive functions
- 2. a mixed effect model with variation between and within AN synaptopathy groups and OHC dysfunction groups (individual subjects will be considered as random) will be used to calculate:
 - a. the percent of variance contribution to HIN function
 - b. the variance component ratio of OHC dysfunction vs. AN dysfunction
- 3. univariate and multivariate models will be applied to the data as described in Specific Aim 1.1 to determine the relationship between mean HIN performance and the other independent

variables (Table 3) in all subjects in order to identify statistically significant factors that contribute to HIN performance

Power analysis: Using a mixed effect model with two OHC groups (Groups 2, 5; n=100 per group), two AN synaptopathy groups (Groups 1, 4; n=100 per group), and two mixed OHC and AH groups (Groups 3, 6; n=100 per group), we will be able to detect a minimum detectable variance component ratio of 0.45 on a continuously measured primary outcome with power of 80%.

Specific Aim 2: to determine whether specific strategies employed by HAs to optimize HIN performance effectively compensate for either OHC or AN dysfunction

n = 1,000 subjects

Statistical Methods: described in detail in the Data Analysis section of the Research Strategy.

- 1. subjects will be rank ordered by _{hf}PTA, and correlations will be calculated between _{hf}PTA and the remaining variables

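### Aim 2's detectable interaction effect of 0.325 SD (0.054 microvolts) does not follow from 100 subjects per cell; a two-group interaction needs about 0.56 SD (0.093 microvolts)

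*SAP*

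**What the plan says.** The opening paragraph of the SAP explains how every detectable effect was obtained: "The sample size was fixed and detectable EF (or Cohen's D) was calculated". The raw-unit difference was then "calculated by multiplying EF and SD for the outcome measure". An EF is therefore a mean difference in SD units.

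For Specific Aim 2 the total is "n = 1,000 subjects". The Power analysis paragraph takes mean CAP amplitude as the primary outcome (SD 0.166) and specifies "two hundred (200) subjects per group with equal (100) number of subjects with or without difficulty HIN". It says the design will "detect 0.28 EF difference among groups with 80% power and a significance of 0.05". Its last sentence adds: "For the experimental group and HIN difficulty interactions, we will be able to detect an EF of 0.325 which is equivalent to 0.054" microvolts.

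The planned model is ANCOVA: "ANCOVA will be run to compare these variables among HA feature or control groups". No covariate R-squared is given, and the interaction contrast is not defined.

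**The concern.** An interaction is estimated less precisely than a main effect from the same subjects. With equal cells, a two-group by two-level interaction expressed as a difference of differences has twice the standard error of the main-effect comparison, so its detectable size should be twice as large. The plan's interaction figure is only 0.325/0.28 = 1.16 times its main-effect figure. It is even smaller than the difference detectable between two single cells of 100.

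The interaction asks whether differences between hearing-aid feature groups depend on HIN difficulty. As written, the plan suggests 80% power for an interaction of 0.054 microvolts. If the true power is far lower, a non-significant interaction could be misread as evidence against an effect of that size.

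**Working it through.** **Inputs.** From Specific Aim 2: 100 per group-by-HIN cell, 200 per group, SD 0.166, 80% power, alpha 0.05. From the SAP's opening paragraph: EF is Cohen's d, and the raw difference is EF × SD. Assumptions: the test is two-sided, the 80% and 0.05 carry over to the interaction sentence, cells are independent with a common SD, and there is no covariate gain.

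**Formula.** Detectable EF = (1.960 + 0.842) × SE, with SE in SD units. Exact values use the noncentral t.

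**Step 1: reproduce the plan's other figures.**
- Aim 1.1, 26 v 26: noncentral t gives 0.792 (plan: 0.8).
- Aim 2, 200 v 200: SE = √(2/200) = 0.10, so 2.802 × 0.10 = 0.280; noncentral t 0.281 (plan: 0.28).
- Conversion: 0.325 × 0.166 = 0.054, as stated.

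Two-sided 0.05, 80% power and no covariate adjustment are therefore the settings that return the plan's own numbers.

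**Step 2: two-group interaction.** The contrast is (A with difficulty − A without) − (B with − B without).
- SE = √(4/100) = 0.20.
- Detectable EF = 2.802 × 0.20 = 0.560; noncentral t 0.562.
- In raw units: 0.562 × 0.166 = 0.093 microvolts.
- Ratio to the stated figure: 0.562/0.325 = 1.7.
- Power at 0.325: Φ(0.325/0.20 − 1.960) = Φ(−0.335) = 37%.
- Cell size for 80% power at 0.325: 4 × (2.802/0.325)² = 297.2, so 298 per cell (596 per group).

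**Step 3: other contrasts, two-sided.** The pooled rows assume five groups, inferred from 1,000/200.

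| Contrast | SE | Detectable EF at 80% | Power at 0.325 |
|---|---|---|---|
| Two-group difference of differences | 0.200 | 0.562 | 37% |
| One group v the other four | √(2/100 + 2/400) = 0.158 | 0.443 | 54% |
| Two groups v three | √(2/200 + 2/300) = 0.129 | 0.362 | 71% |
| Simple 100 v 100 (not an interaction) | √(2/100) = 0.141 | 0.398 | 63% |

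The overall five-group interaction F-test has 4 df, with noncentrality 50 × Σ(Dg − D̄)², where Dg is the with-minus-without difference in group g. For a largest gap of 0.325, power runs from 22% to 49% depending on the pattern. The gap detectable at 80% power runs from 0.45 to 0.69 SD.

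**Step 4: could covariates close the gap?** The two-group contrast would need R² = 1 − (0.325/0.562)² = 0.67. The same R² would reduce the main-effect figure to 0.281 × √(1 − 0.67) = 0.16, but the plan states 0.28.

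**Step 5: where might 0.325 come from?** The SAP does not say. These calculations come close:
- 200 v 200 at 90% power: 0.3249.
- 200 v 200 at 80% power with alpha 0.05/3: 0.3247.
- One cell of 100 v the other three cells of a 2 × 2: 0.324.

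The first two are main-effect comparisons, and the third is not an interaction.

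**The case against.** The interaction sentence states no power, alpha, sidedness or contrast, and Aim 2's methods are said to be detailed in a Research Strategy that is not at hand. The contrast may be defined there. The 37% belongs to the two-group contrast, which is the least favourable of the 1-df contrasts tried. Pooling two groups against three gives 71% power and a detectable 0.362, about 11% above 0.325. ANCOVA is planned, and for that contrast an R² of 1 − (0.325/0.362)² = 0.19 would be enough (0.46 for one group v four). A one-sided test of two groups v three would detect 0.321, just inside the stated figure. If EF meant half the difference of differences, 0.325 would have about 90% power. Finally, the listed Aim 2 analyses name no interaction test, so the practical harm is limited.

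Some of this stands. The size of the shortfall depends on a contrast the SAP does not define, and 37% must be tied to two groups. But none of these readings yields 0.325 from the stated inputs:
- The one-sided pooled reading needs a grouping and a sidedness that the SAP does not state, and the companion figures 0.8 and 0.28 match two-sided tests.
- An R² of 0.19 would also reduce 0.281 to about 0.25, which is not what the plan reports.
- Half-scaling gives 0.28 at 80% power, not 0.325. It would also make the interaction itself 2 × 0.054 = 0.108 microvolts.

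**Conclusion.** The concern holds. At two-sided 0.05 and 80% power, with EF as the SAP defines it and no covariate gain, no interaction contrast examined is detectable at 0.325 SD. For two groups the figure should be 0.56 SD (0.093 microvolts), and power at the stated effect is about 37%. Across the 1-df interaction contrasts tried, the detectable size is 0.36 to 0.56 SD and power at 0.325 is 37% to 71%; the pooled values rest on the inferred five groups. The carry-over of 80% and 0.05 is an assumption, though the natural reading of the paragraph. This should be fixed, because a stated sensitivity is wrong as written. It does not affect the group-comparison figure of 0.28, which is right for one comparison of two groups of 200.

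**What to change.** In the Aim 2 Power analysis, name the interaction contrast and state its power, alpha and sidedness. If it compares two groups, replace the 0.325 and 0.054 figures with wording such as: *a two-group difference-in-differences of 0.56 SD (0.093 microvolts on CAP amplitude) with 80% power at two-sided 0.05*. If another contrast, power, alpha or covariate R² was intended, state it and show that it gives the quoted value. Label 0.28 as the figure for a single comparison of two groups of 200.

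The cost is a revision of one paragraph and a less favourable stated sensitivity for the interaction. The sample size was fixed first and EF derived from it, so enrolment does not change.
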